Hypothesis 1A: We hypothesize that an enhanced version of the SleepTrackTXT tool that includes sleep health and sleep quality components will contribute to significant reductions in intra-shift fatigue.

Aim 2: To determine the impact of the SleepTrackTXT intervention on sleep quality and sleep health indicators including hours of sleep and recovery between shift work.

Rationale Aim 2: Preliminary findings from our pilot randomized trial using an Intent-To-Treat analysis shows a statistically significant improvement in sleep quality among participants in the intervention group. The improvement fell short of a cut point thought to be clinically meaningful. We believe an enhanced intervention focused on sleep debt may have a greater impact on sleep quality.

Hypothesis 2A: We believe an enhanced version of our brief SleepTrackTXT intervention that includes a sleep health and sleep quality component can lead to clinically meaningful improvements in sleep quality over time.

Our power calculation was designed to determine the number of subjects needed to detect a clinically meaningful difference of 3 points on the PSQI from baseline to the study end. We fixed alpha at 0.05 and performed one-sided hypothesis testing. The standard deviation of the difference was estimated as 2.2 using data from our recent randomized trial.[5] Group sample sizes of 27 for the intervention and 27 for the control group achieve 90% power to reject the null hypothesis of equal means with a standard deviation of 2.2 and significance level of 0.05 using a two-sided two-sample equal variance t-test. We estimate a 15% attrition rate based on our prior randomized trial.[23] We estimate 15% of participants in the intervention group will not abide by the intervention protocol. Based on these estimates, we seek to enroll a total of n=100 (50 per group) to account for attrition and non-compliance.

Research Protocol, Part Three – Methods (3000 characters):

STUDY DESIGN: We will use a two-arm parallel, randomized, controlled and single-blinded trial. Our design is similar to the original SleepTrackTXT trial with 100 EMS clinicians.[5, 23]

SETTING AND POPULATION: We will recruit and enroll study participants from four air-medical EMS organizations: 1) Carolina's MedCenter Air; 2) STAT MedEvac; 3) MedFlight of Ohio, and 4) MercyFlight of Buffalo, NY.

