Site 4: Mercy Flight of Buffalo, NY. Mercy Flight operations are conducted from three bases (Buffalo, Olean and Batavia), 24 hours a day / 7 days a week. The Mercy Flight Team consists of 26 paramedics, 27 nurses, 13 pilots, 9 air medical communications specialists, 6 aircraft mechanics and an 11 member administrative, development, finance and facilities management team that provides the necessary support service for flight operations. Each helicopter crew consists of a Pilot, Paramedic and Nurse. Flight Paramedics have at least two years of high volume, critical care EMS experience. Flight Nurses have more than 2 years of critical care experience in an Emergency Room (ER), Intensive Care Unit (ICU) or other critical care field. Over the past 30+ years, Mercy Flight has conducted more than 20,000 patient missions and thousands of Ground Crew Safety Training and Community Education sessions throughout its primary service area of Western New York, Northwest Pennsylvania and Southern Ontario. The dispatch center is staffed 24/7 by Communications Specialists who field, prioritize, dispatch and coordinate incoming flight requests. They are certified by the National Association of Air Medical Communication Specialists (NAACS). Mercy Flight a Part 145, FAA Certified Repair Station and our in-house aircraft mechanics utilize more than 100 years of combined experience to keep the helicopters flight-ready.

PROTOCOL: We will recruit via email and study flyers sent directly to eligible individuals employed at the study sites. We seek to enroll n=100 clinicians. Clinicians with an interest in the study will complete a telephone screening appointment. Inclusion criteria include: 1) 18 years of age and older, 2) working clinically at a study site, 3) currently working in shifts, 4) has a smartphone, and 5) willing to take part in a research study that requires the sending and receiving of multiple text messages daily over 4-months. Eligible clinicians will complete a standard enrollment process with an IRB-approved informed consent procedure.

Randomization into the intervention versus control groups will occur immediately after completion of informed consent. All consented participants will receive a unique login account to access the study website. Participants will use the secure study website to document shift schedules for four months. Participants will receive \$100 remuneration.

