CONTROL GROUP: The control group participants will use an online sleep diary, a shift scheduling tool to document shift schedules, answer text-message queries about their fatigue and sleep health between shifts (inter-shift) and during shiftwork (intra-shift). The intra-shift text-messages are modeled after the original SleepTrackTXT trial (clinicaltrials.gov identifier: NCT02063737). Control group participants will receive inter-shift messages on days off from work at noon (12:00pm). These inter-shift messages will query the participant's sleep obtained, perceived recovery since last shift, fatigue, sleepiness, and difficulty with concentration. A select group of n=10 control group participants will wear wrist actigraphy for purposes of validating self-reported sleep diary information. This same select group of 10 control group participants will be asked to complete psychomotor vigilance tests (PVTs) at the beginning and end of a select number of shifts during the study period.

Research Protocol, Part Four – Outcome Measures & Data Analysis (3000 characters):

One outcome of interest (linked to Aim 2) is sleep quality, which will be measured with the widely used Pittsburgh Sleep Quality Index (PSQI).[19] A PSQI score of 6 or more on a 21-point scale indicates poor sleep quality. A reduction in PSQI of 3-points suggests a clinically meaningful improvement in sleep quality.[22] We will administer the PSQI at baseline and then again at the end of the 4-month study period.

Our power calculation was designed to determine the number of subjects needed to detect a clinically meaningful difference of 3 points on the PSQI from baseline to the study end. We fixed alpha at 0.05 and performed one-sided hypothesis testing. The standard deviation of the difference was estimated as 2.2 using data from our recent randomized trial.[5] Group sample sizes of 27 for the intervention and 27 for the control group achieve 90% power to reject the null hypothesis of equal means with a standard deviation of 2.2 and significance level of 0.05 using a two-sided two-sample equal variance t-test. We estimate a 15% attrition rate based on our prior randomized trial.[23] We estimate 15% of participants in the intervention group will not abide by the intervention protocol. Based on these estimates, we seek to enroll a total of n=100 (50 per group) to account for attrition and non-compliance.

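### With no minimum PSQI at entry, a mean effect below 3 points could not be read under Hypothesis 2A as too weak rather than as little room to improve

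*Combined protocol and SAP*

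**What the plan says.** Part Two states Hypothesis 2A: the enhanced tool "can lead to clinically meaningful improvements in sleep quality over time". Part Four supplies the cut point and the yardstick: "A PSQI score of 6 or more on a 21-point scale indicates poor sleep quality. A reduction in PSQI of 3-points suggests a clinically meaningful" gain. The sample-size paragraph, which appears in both Parts, aims to "detect a clinically meaningful difference of 3 points on the PSQI from baseline to the study end".

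Eligibility is in Part Three: "Inclusion criteria include: 1) 18 years of age and older, 2) working clinically at a study site, 3) currently working in shifts", followed by having a smartphone and being willing to text over four months. None of the five criteria concerns sleep quality.

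The only PSQI comparison named is a two-sample t-test of equal means, and it is named only inside the sample-size paragraph. The linear mixed model in Part Four is for end-of-shift fatigue. A general sentence there on parametric and non-parametric tests of change does not mention baseline PSQI. For Aim 2 the plan gives no baseline adjustment, interaction, poor-sleeper analysis or responder definition.

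On the pilot's PSQI result, the Rationale for Aim 2 reports a statistically significant gain but adds: "The improvement fell short of a cut point thought to be clinically meaningful".

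**The concern.** The 3-point benchmark is a fall on a scale where lower is better, and by the plan's own cut point a score of 0–5 is already not poor sleep. Participants in that range have limited room to show the change that Hypothesis 2A is about. An average over everyone mixes them with poor sleepers, for whom 3 points is readily attainable on the scale.

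If the trial found a mean effect of, say, 2 points, two explanations would fit equally well: the programme is too weak, or it works as hoped in poor sleepers and the others could not move much. These lead to different decisions about the tool. The sponsor's account of the pilot shows that an average can indeed be set against the 3-point mark. In addition, the source cited for that mark (reference 22) is, by its title, a trial in older people with chronic insomnia, whereas clinicians here are not selected for poor sleep.

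**Working it through.** **Inputs from the plan.** Benchmark 3 points; poor sleep at PSQI 6 or more; SD of the difference 2.2; two-sided alpha 0.05 (the same paragraph also says one-sided); 27 per group for 90% power; 50 enrolled per group; 15% attrition. Evaluable per arm: 50 × 0.85 = 42.5, taken as 42.

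**Assumptions.** The scale minimum is 0. The share of poor sleepers, p, is 50–80%; Part One says only that many EMS workers report poor sleep quality. Gains are relative to control, with control scores unchanged on average.

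**The plan's own figure.** For a difference of 3, SD 2.2, two-sided 0.05 and 90% power, the t-test needs 13 per group, not 27. At 27 per group, power for 3 points is 99.8%. The stated 27 fits a 2-point difference (90.6% power). That is a separate matter, but it shows that the test has power to spare at 3 points.

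**Room to improve.** A baseline of 0, 1 or 2 can fall by at most 0, 1 or 2. A baseline of 3, 4 or 5 can fall by 3, to 0, 1 or 2. If good sleepers were spread evenly over 0–5 and each fell as far as possible up to 3, their mean gain would be (0 + 1 + 2 + 3 + 3 + 3)/6 = 2.0. So a mean good-sleeper gain, g, of 0–2 is examined.

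**Dilution.** If every poor sleeper gains 3, the overall mean is 3p + g(1 − p):

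| p | g = 0 | g = 1 | g = 2 |
|---|---|---|---|
| 50% | 1.5 | 2.0 | 2.5 |
| 60% | 1.8 | 2.2 | 2.6 |
| 70% | 2.1 | 2.4 | 2.7 |
| 80% | 2.4 | 2.6 | 2.8 |

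**Overall and subset estimates on the same two yardsticks.** The standard error is 2.2 × √(2/n): 0.48 with 42 per arm and 0.68 with 21 per arm (half of 42, so p = 50%).

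| | Overall, true 1.5 | Overall, true 2.0 | Poor sleepers, true 3 |
|---|---|---|---|
| n per arm | 42 | 42 | 21 |
| Power against zero | 87% | 98% | 99% |
| Chance that the estimate is 3 or more | 0.1% | 1.9% | 50% |
| 95% CI half-width | 0.96 | 0.96 | 1.37 |

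**Sensitivity at the low end (p = 50%, g = 0).** If the spread in gains is added to the SD in both arms, the SD is √(2.2² + 0.5 × 0.5 × 3²) = 2.66 and overall power is 72%. If instead the 15% of intervention participants expected not to comply gain nothing, the effect is 1.5 × 0.85 = 1.275 and power is 75%.

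**The case against.** The strongest reply is that no sentence makes success depend on an observed mean of 3. In the plan, 3 points is the design difference, and the test is of equal means. A reader might infer that the trial is set up to fail Hypothesis 2A, or quote the under-2% chance of an overall estimate reaching 3. The documents do not support that: such a decision rule is not written down, and by the same measure a poor-sleeper subset with a true effect of exactly 3 would reach 3 only half the time. A reader might also infer that a floor explains the pilot's shortfall. Part Two does not say so; its response is a component on sleep debt.

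The size of the dilution is also assumed. If most participants are poor sleepers and those scoring 3–5 improve, the shortfall is 0.2–0.5 points, well inside the overall half-width of 0.96. Poor sleepers with high scores could gain more than 3. Lastly, Part Six addresses the whole medical transport workforce, for which the average over all participants is a legitimate quantity.

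All of this stands as a limit on the point. It leaves untouched that nothing in the plan would let a reader tell the two explanations of a mean below 3 apart.

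**Conclusion.** The concern holds as one of interpretation. For any poor-sleeper share below 100% and any mean good-sleeper gain below 3, an effect of exactly 3 in every poor sleeper gives an overall mean below 3. Under the assumed ranges it is 1.5–2.8. The documents do not show where in that range the trial would fall. The calculation also rests on unchanged controls: improvement in controls would lower the between-arm difference, and worsening would raise it.

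A reader might go further and conclude that the PSQI test is invalid or underpowered. That is not supported. Its type I error is unaffected, and at the plan's SD it has about 87–98% power for 1.5–2.0 points; it drops to 72–75% only under the least favourable added assumptions. What is missing is a pre-specified way to relate the result to the 3-point benchmark among people for whom that benchmark is attainable.

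**What to change.** In Part Four:

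- State the between-arm PSQI comparison in all randomised participants as the main Aim 2 test, adjusted for baseline PSQI.
- Pre-specify a supportive analysis that reports the arm-by-baseline-PSQI interaction and the between-arm difference with 95% CI among participants with baseline PSQI of 6 or more, read against 3 points.
- State that the baseline PSQI is completed before allocation. Part Three randomises directly after consent and does not say when the baseline PSQI is taken, so as written the subset could be defined by a self-report given after allocation.

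Eligibility and enrolment stay as they are. The cost is about a paragraph of text, using a score already collected, and possibly a change in the order of enrolment steps. Because the subset contrast is between randomised arms, regression to the mean among high scorers should affect both arms alike.

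The downside is precision. With 21 per arm the half-width is about 1.4 points against 0.96 with 42, if SD 2.2 also holds in poor sleepers, which the documents do not show. A subset estimate of 3 would carry an interval of about 1.6 to 4.4. The analysis helps interpretation and cannot by itself establish that the effect is at least 3.

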One outcome measure is linked to Aim 1 and is intra-shift fatigue reported at the beginning, during, and end of scheduled shifts. We will use a single-item measurement of fatigue, which is the preferred approach for research that involves real-time data capture and/or ecological momentary assessment (EMA).[20] This measure was constructed based on prior EMA research of insomnia, it has been tested in our pilot trial and shown to be sensitive to change in fatigue over the course of shift work.[21] We hypothesize that over time and after repeated exposure to the intervention, participants in the intervention group will report lower levels of fatigue at the end of shift than participants in the control group.

We will use linear mixed-model analyses to examine the effectiveness of the intervention on reducing reported fatigue at the end of shift among participants in the intervention group and compare reported values to the control group. We will construct a model where the outcome is the reported fatigue at the end of each shift, a fixed effect of time in study, and a random effect for participants to account for multiple shifts within each person. We will examine the estimated change in fatigue per shift and over multiple shifts throughout the study period. Post-estimation testing will be used to describe the correlation in fatigue scores within the subjects across shifts.

Independent measures of interest include age, sex, health status indicators, and other demographic and person-level variables that address employment status, shift schedule/pattern, general fatigue, co-morbidities/diagnoses, and psychosocial factors that may be associated with sleep and shiftwork. We will use descriptive statistics to examine the distribution of these variables, parametric and non-parametric tests to assess change in values/scores on measures that may change over the course of the 4-month study period.

Research Protocol, Part Five – Limitations (3000 characters):

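### The stated 90% power does not follow from the stated inputs (3 PSQI points, SD 2.2, 27 per group give over 99%), and the test is called both one-sided and two-sided

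*Combined protocol and SAP*

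**What the plan says.** The same paragraph appears in the combined protocol and SAP under Research Protocol, Part Two (Objectives Hypotheses) and Part Four (Outcome Measures & Data Analysis).

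- **Target:** the calculation was meant to "detect a clinically meaningful difference of 3 points on the PSQI from baseline to the study end". Just before the paragraph, Part Four explains the 3 points: "A reduction in PSQI of 3-points suggests a clinically meaningful improvement in sleep quality".
- **Error rate and sidedness:** "We fixed alpha at 0.05 and performed one-sided hypothesis testing". The later sentence that gives the power has "significance level of 0.05 using a two-sided two-sample equal variance t-test".
- **Spread:** "The standard deviation of the difference was estimated as 2.2 using data from our recent randomized trial".
- **Result:** "Group sample sizes of 27 for the intervention and 27 for the control group achieve 90% power". This sentence gives no difference.
- **Allowances:** 15% attrition, and "We estimate 15% of participants in the intervention group will not abide by the intervention protocol". Enrolment is then set at 100, or 50 per group.

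No expected change in the control group, and no between-group difference other than the 3 points (if they are meant as one), appears anywhere in the document.

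**The concern.** A 3-point difference against an SD of 2.2 is a standardised effect of 3/2.2 = 1.36. That is very large, and a two-sample t-test with 27 per group should detect it almost always, so 90% looks too low for the stated inputs. Separately, one calculation cannot be both one-sided and two-sided at alpha 0.05.

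Two things are at stake. First, this paragraph is the only justification of the sample size, and a reader cannot tell from it which between-group difference the trial is sized to detect. Hypothesis 2A is about clinically meaningful improvement, so it matters whether that difference is 3 points or something smaller. Second, this is the only place that names a between-group test for the PSQI. The rest of Part Four offers only "parametric and non-parametric tests to assess change in values/scores on measures". The conflict over sidedness therefore leaves the rejection rule open: a one-sided p of 0.03 (two-sided 0.06) would succeed under one sentence and fail under the other.

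**Working it through.** **Inputs, all from the sample-size paragraph:** difference Δ = 3 points; SD σ = 2.2; alpha 0.05; n = 27 per group, 1:1; two-sample equal-variance t-test; stated power 90%.

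**Formula.** Noncentrality λ = Δ / (σ√(2/n)), with 2n − 2 degrees of freedom. Power is the probability that a noncentral t with parameter λ exceeds the critical value; for the two-sided test the far tail is negligible here.

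**1. The plan's own figure.** λ = 3 / (2.2 × √(2/27)) = 5.01 on 52 degrees of freedom.

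| Test | Critical t | Power at 27 per group | n per group for 90% |
|---|---|---|---|
| Two-sided | 2.007 | 99.84% | 13 (12 gives 89.1%, 13 gives 91.5%) |
| One-sided | 1.675 | 99.95% | 10 (9 gives 86.9%, 10 gives 90.1%) |

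A simulation of the two-sided test (200,000 runs) also gives 99.84%. The normal approximation gives 99.89% two-sided and 99.96% one-sided. The 90% is not reproduced, and 27 is at least twice the number that the inputs call for, so rounding does not explain the gap.

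**2. Other readings that keep 3 points.**

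| Reading | Two-sided | One-sided |
|---|---|---|
| SD 2.2 × √2 = 3.11 | 93.5% | 96.8% |
| SD 2 × 2.2 = 4.4 | 69.1% | 79.6% |
| 27 in total (13 and 14) | 92.5% | 96.4% |
| Paired test, 27 people | >99.99% | >99.99% |
| Effect cut by 15%, to 2.55 | 98.7% | 99.5% |
| Effect cut by 30%, to 2.1 | 93.1% | 96.5% |

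None gives 90%. To get 90% at 3 points with 27 per group, the SD would have to be 3.34 two-sided or 3.72 one-sided.

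**3. What would give 90% with 27 per group and SD 2.2.** Solving for the difference gives 1.98 points two-sided or 1.78 one-sided. A round 2.0 points, two-sided, has λ = 2 / (2.2 × √(2/27)) = 3.34; 26 per group give 89.5% and 27 give 90.6%, so 27 is exactly the required number. One-sided, 2.0 points would need only 22 per group (21 gives 89.4%, 22 gives 90.7%). So 2.0 points fits 27 only as a two-sided test.

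**4. What the enrolled number supports.** 50 × 0.85 = 42.5, so about 42 completers per arm. At SD 2.2, two-sided:

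- power for 3 points is 99.999%;
- the difference detectable with 90% power is about 1.6 points (1.57), before any allowance for non-compliance.

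The paragraph does not say how non-compliance enters. If 15% of the intervention arm are analysed as randomised and gain nothing (an assumed model), 3 points becomes 3 × 0.85 = 2.55. Power is then 99.95%, or 99.85% by simulation when the added spread from mixing compliers and non-compliers is included. The 90% detectable difference becomes 1.57/0.85 = 1.85 without that added spread, and about 1.9 points with it.

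**5. From 27 to 50.** 27/0.85 = 31.8 (32 per group) for attrition alone. Dividing again by 0.85 gives 37.4 (38). Using 0.85² for non-compliance, 27/(0.85 × 0.85²) = 43.96 (44). None reaches 50, and the step is not shown.

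**The case against.** The strongest reply is that the 3 points were never a between-group difference. They are tied to change from baseline and to a reduction in score, Hypothesis 2A speaks of improvement over time, and the sentence with 27 and 90% names no difference. On that view 99.8% comes from putting a within-person change into a between-group test, and the real fault is an omitted input, probably 2.0 points. The reading is plausible and fits the figures closely. But 2.0 appears nowhere in the document, and the paragraph opens by presenting 3 points as what the calculation was designed to detect. If the reading is right, the one input that fixes the sample size is missing and another stands in its place. The paragraph needs correcting either way.

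A second reply is that the mismatch is harmless, because 27 is more than 3 points requires and 50 per group will be enrolled. That stands as far as adequacy for 3 points goes, and it limits the severity.

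A third is that the PSQI rejection rule is open mainly because Part Four sets out no between-group PSQI analysis, so tidying the power paragraph would not by itself supply one. This is fair, and it is why the chosen sidedness has to be stated for the analysis as well. The one sentence that names a test says two-sided, and the 2.0-point reading agrees with it. That suggests the one-sided phrase is the stray one, but nothing in the document confirms it.

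**Conclusion.** The concern holds on both counts. With the only difference stated, 27 per group give 99.84% power two-sided or 99.95% one-sided against a stated 90%; 90% would need 13 or 10 per group. The same paragraph calls the test one-sided and two-sided, and no other section resolves it. These figures assume an equal-variance two-sample t-test with 2.2 as the SD of individual change in each arm.

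The explanation that fits best, an unstated between-group difference of about 2.0 points tested two-sided, remains an inference. Which entry is wrong or missing can be settled only from the source calculation. This is a defect in the stated justification and in the test's definition, not a shortage of participants for a 3-point difference. It should be fixed before analysis.

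**What to change.** In both places where the paragraph appears:

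1. Check the source calculation and restate the between-group difference, SD, power and n so that they reproduce. Keep the 3-point within-person change separate from the between-group difference. If SD 2.2 and two-sided testing are confirmed, the text could read: *27 per group give 90% power for a between-group difference of about 2.0 points and over 99% for 3 points; about 42 completers per arm give 90% power for about 1.6 points before any allowance for non-compliance.*
2. Choose one sidedness, and state it both in the power statement and for the between-group PSQI test in Part Four.

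Optionally, show how 27 per group became 50.

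The cost is checking one calculation and rewording one paragraph that is printed twice, plus a sentence on the PSQI test. Enrolment, conduct and outcomes do not change.

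### Aim 2: comparing month-4 PSQI with adjustment for the baseline PSQI already collected would usually narrow the confidence interval, at almost no cost

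*Combined protocol and SAP*

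**What the plan says.** Part Four (Outcome Measures & Data Analysis) of the combined protocol and SAP makes the PSQI the Aim 2 outcome and sets two assessments: "We will administer the PSQI at baseline and then again at the end of the 4-month study period".

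The power paragraph, which appears in both Part Two and Part Four, targets "a clinically meaningful difference of 3 points on the PSQI from baseline to the study end" and adds: "The standard deviation of the difference was estimated as 2.2 using data from our recent randomized trial". The test it names has a "significance level of 0.05 using a two-sided two-sample equal variance t-test". Read together, these phrases point to a two-sample comparison of change scores, although the paragraph is a sample size justification and not an analysis section.

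Two other pieces of analysis text exist in Part Four:

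- The linear mixed model has end-of-shift fatigue as its outcome, so it serves Aim 1 only.
- The closing sentence promises "parametric and non-parametric tests to assess change in values/scores on measures that may change over the course of the 4-month study period". It follows a list of independent measures and names neither the PSQI nor a particular test.

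Nowhere is baseline PSQI entered as a covariate.

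**The concern.** Under randomisation a change-score t-test gives an unbiased estimate, so this is an improvement and not the correction of an error. Baseline is already used, by subtraction. Subtraction assumes that one extra point at baseline carries over as one extra point at month 4. When the true slope is below 1, the change score over-corrects, and its estimate moves with any chance difference in baseline PSQI between the arms. A baseline-adjusted model estimates the slope from the data and removes that source of variation.

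What is at stake is precision. Rationale Aim 2 in Part Two reports that the pilot's effect on sleep quality was statistically significant, but "The improvement fell short of a cut point thought to be clinically meaningful". Hypothesis 2A is about a clinically meaningful improvement. The size of the effect therefore matters as well as its significance, and the interval width bears on size directly.

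**Working it through.** **Inputs from the plan (Part Four).** Difference 3 points; SD of change 2.2; two-sided alpha 0.05; 27 per arm for a stated 90% power; 50 per arm enrolled; 15% attrition. Completers per arm: 50 × 0.85 = 42.5, taken as 42.

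**Assumed, because the documents do not give them.** The correlation r between baseline and month-4 PSQI (0.3, 0.5, 0.7, with 0.9 as a high case) and, at first, equal variances at the two visits.

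**The plan's own figure.** With 27 per arm the noncentrality is 3 / (2.2 × √(2/27)) = 5.01 on 52 df, which gives two-sided power of 99.8%. The stated 90% is not reproduced from these inputs. That is a separate matter; here it means only that the case for adjustment cannot rest on power.

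**Change-score analysis, 42 per arm.**
- SE = 2.2 × √(2/42) = 0.480.
- Half-width = t(0.975, 82) × 0.480 = 1.989 × 0.480 = 0.955 points.

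**Baseline-adjusted analysis, 42 per arm.**
- SD at one visit = 2.2 / √(2(1 − r)).
- Residual SD = SD at one visit × √(1 − r²).
- Estimating the slope inflates the variance by 1 + 1/(2n − 4) = 1 + 1/80 = 1.0125.
- Half-width = t(0.975, 81) × residual SD × √(2/42) × √1.0125.
- Variance ratio to the change score = 1.0125 × (1 + r)/2.
- Equivalent change-score sample size = 42 / variance ratio.

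| r | SD at one visit | Residual SD | Half-width | Narrower by | Variance ratio | Equivalent n per arm |
|---|---|---|---|---|---|---|
| 0.3 | 1.86 | 1.77 | 0.775 | 19% | 0.658 | 64 |
| 0.5 | 2.20 | 1.91 | 0.832 | 13% | 0.759 | 55 |
| 0.7 | 2.84 | 2.03 | 0.886 | 7% | 0.861 | 49 |
| 0.9 | 4.92 | 2.14 | 0.937 | 2% | 0.962 | 44 |

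With equal variances the two analyses have the same variance at r = 2/1.0125 − 1 = 0.975 (at 27 per arm, 2/1.02 − 1 = 0.961).

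**Unequal variances.** Let k be month-4 SD divided by baseline SD. The variance ratio is 1.0125 × k²(1 − r²) / (1 + k² − 2rk).

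| k | r = 0.3 | r = 0.5 | r = 0.7 |
|---|---|---|---|
| 1.25 | 0.79 | 0.90 | 0.99 |
| 0.8 | 0.51 | 0.58 | 0.64 |

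At k = 1.25 the true slope rk equals 1 when r = 0.8. There the change score is already the best linear adjustment, and the ratio is 1.0125.

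**Chance imbalance.** A baseline difference of one standard error (0.41, 0.48 and 0.62 points at r = 0.3, 0.5 and 0.7, equal variances) moves the change-score estimate by (1 − r) times that difference on average: 0.28, 0.24 and 0.19 points. The adjusted estimate does not move. This is the same variance seen conditionally, not a further loss.

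**Simulation** (20,000 replicates for each r of 0.3, 0.5, 0.7 and 0.9; true difference −3). Mean estimates were −2.99 to −3.00 and coverage was 95% for both methods. Variance ratios were 0.66, 0.77, 0.86 and 0.96. The adjusted interval was the narrower one in 100%, 99.9%, 98% and 74% of replicates.

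**The case against.** The strongest reply is that nothing is wrong with the planned test and that the gain is small in absolute terms: 0.18, 0.12 or 0.07 points of half-width at r = 0.3, 0.5 or 0.7, against a 3-point threshold on a 21-point scale. No conclusion is shown to change. This is true, and it is why the point is an improvement and not a defect.

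The gain also depends on quantities the documents do not give. If PSQI variability rises by a quarter during the study, the gain vanishes at about r = 0.72, and from there to about r = 0.85 adjustment costs a little. That stands, but the worst cost is about 1.2% of the variance, against savings of 14% to 34% under equal variances for r between 0.7 and 0.3.

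The comparator is inferred from a power paragraph. This also stands. With no Aim 2 analysis written, however, a sentence has to be added in any case, and it may as well name the more precise analysis.

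The clinical threshold is worded as a within-person fall: "A reduction in PSQI of 3-points suggests a clinically meaningful improvement in sleep quality". Adjustment sharpens the between-group difference only; the mean change in each arm gains nothing. Both should be reported.

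Finally, the cost is not strictly nil if the baseline PSQI is at present completed after randomisation, since the enrolment order would then change. The documents do not say. The figures also assume 42 completers per arm, from "We estimate a 15% attrition rate based on our prior randomized trial", and the proposed model does not settle how missing month-4 scores are handled.

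**Conclusion.** The point holds as a low-cost improvement that should be made. The plan collects baseline PSQI, states no Aim 2 model, and ties the PSQI to a two-sample t-test that reads as a comparison of change scores. Replacing that with a baseline-adjusted comparison would be expected to narrow the 95% interval by 7% to 19% for correlations from 0.7 down to 0.3, and by about 2% at 0.9. These percentages assume equal variances at the two visits and do not depend on the SD of change; the half-widths in points rest on SD 2.2 and 42 completers per arm. If the month-4 SD is higher than the baseline SD, the gain is smaller and can be nil; if lower, it is larger. Neither the validity nor the power of the planned comparison is in question.

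**What to change.** In Part Four, after the description of the PSQI, add text such as:

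> Aim 2 will be analysed with a linear model of month-4 PSQI on randomised group and baseline PSQI, with participants analysed as allocated. We will report the adjusted between-group difference with its 95% CI, alongside the mean change from baseline in each arm.

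The per-arm changes are included because the plan expresses its 3-point threshold as a reduction.

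In the Protocol paragraph of Part Three, which places randomisation directly after consent, state that the baseline PSQI is completed before allocation. No section gives its timing, and a covariate should precede allocation. This sentence is secondary; the precision argument does not depend on it.

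Cost: one degree of freedom, already counted in the half-widths above, and about three sentences. No new data, visits or participants are needed, though the order of enrolment steps would have to change if the baseline PSQI currently follows randomisation.
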